2.2. Estimands

2.2.1. Primary estimand

Vitreous haze (VH) 0 response rate in DE-109 440 μ g group vs. Sham group at Month 5 in all study eyes that received at least one dose of the study treatment where all eyes that were rescued due to worsening of uveitis or discontinued from the study due to lack of efficacy or due to adverse events before Month 5 will be treated as non-responders. For study eyes that were rescued for any other reasons or had missing data due to other reasons, imputation by the multiple imputation-based approach will be used.

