3. STUDY DESIGN

3.1. General Study Design

This is a Phase III study to assess the efficacy and safety of DE-109 440 μ g every 2 months in subjects with active, non-infectious uveitis of the posterior segment of the eye (NIU-PS). The 12-month study consists of a 6-month, randomized, double-masked, parallel design, sham-controlled evaluation of DE-109 440 μ g every 2 months followed by a 6-month, open-label period in which all subjects will receive DE-109 440 μ g every 2 months (Figure 1).

Figure 1: Study Design Diagram

The study will begin with a 30-day screening period (Day -30 to Day -1) which will be followed by the 6-month double-masked treatment period. In the double-masked period, approximately 200 eligible subjects will be randomized in a 2:2:1 ratio to three arms:

- 1. **Test arm**: Intravitreal injection of DE-109 440 μg in the study eye(s) every 2 months (Day 1, Month 2, and Month 4) (approximately 80 subjects).
- 2. **Control arm**: Sham procedure administered to the study eye(s) every 2 months (Day 1, Month 2, and Month 4) (approximately 80 subjects). The sham procedure mimics an intravitreal injection without penetrating the eye (the blunt end of an empty syringe is pressed against an anesthetized eye).
- 3. Dummy arm: Intravitreal injection of DE-109 at an undisclosed, fixed dose (within the range of 44 µg to 880 µg) in the study eye(s) every 2 months (Day 1, Month 2, and Month 4) (approximately 40 subjects). This study arm (which has the same route of administration and frequency as the test arm) is included in the study to help ensure masking of treatment assignments. The dose used in this arm will be chosen from a range of DE-109 doses (44 µg to 880 µg) previously demonstrated to have an acceptable safety profile. The dose in this arm will not vary between participating sites or subjects randomized to this arm.

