3.3. Sample Size Planning

Assuming a 30% VH 0 response rate for DE-109 440 μ g group and a 12% response rate for the sham treatment group, 160 subjects (80 subjects per arm) is required to achieve 80% power to detect such a difference in response rate between the DE-109 440 μ g group and the sham treatment group using the Pearson's Chi-square test (two-sided, $\alpha = 0.05$). Including approximately 40 subjects in the dummy arm, a total of approximately 200 subjects with active NIU-PS will be randomized in a 2:2:1 ratio to DE-109 440 μ g, sham, and dummy arms. Because some subjects will contribute two study eyes to this study, the planned sample size of 80 subjects

in both the test (DE-109 440 $\mu g)$ and control (sham procedure) arms will achieve more than 80% power.

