5.4. Multiple Comparisons / Multiplicity

To control the overall Type I error rate associated with the multiple comparisons on the primary and the key secondary endpoints at the 0.05 level (two-sided), the following hierarchical testing strategy will be employed:

- A. Conduct the statistical testing for the primary comparison between DE-109 440 μg and Sham treatment arm on the primary endpoint (VH 0 response) at the significance level of 0.05 (two-sided)
- B. If the result of the primary comparison on the primary endpoint is positive (i.e., *p*-value < 0.05), then conduct the statistical testing for the primary comparison between DE-109 440 μg and Sham treatment arm on the following key secondary endpoints in a hierarchical fashion:
 - 1. Mean composite score at Month 5
 - 2. VH 0 response at Month 3
 - 3. Mean composite score at Month 3

The primary comparison on the $(i+1)^{th}$ key secondary endpoint will be performed inferentially ONLY IF the result of the primary comparison in the ith key secondary endpoint is positive, where i = 1 or 2.

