5.5. Interim Analysis and Data monitoring Committee

An independent data monitoring committee (DMC) whose members will not be participating in the LUMINA study conduct will serve as an advisory board to the Santen senior management team. The DMC will periodically review and make recommendations based on interim data; unmasked data will only be reviewed in closed DMC sessions without participation of Santen personnel. The organization, responsibilities, and procedures of the DMC will be specified in a governing charter.

An interim analysis is planned when the first 100 subjects complete their Month 5 Visit. The DMC is authorized to evaluate unblinded interim efficacy and safety analyses. Study sites will

receive information about interim results only if they need to know for the safety of their patients.

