5.5.1. Interim Analysis

The objectives of the interim analysis are to assess for futility and to re-assess the sample size. No analyses are planned for the purpose of stopping the study early for efficacy. The futility and sample size re-assessment are based on evaluation of conditional power in relationship to pre-specified decision rules defined by ranges of attainable conditional power values under the "promising zone" approach (Mehta et al., 2011). If the conditional power is less than 30%, futility will be recommended and the study may stop for futility. If the conditional power is between 50% and 80%, the sample size will be increased up to 100 extra subjects. If the conditional power between 30% and 50% or greater than 80%, no change to the sample size will take place.

The futility and sample size re-assessment analysis will be evaluated for the primary endpoint, vitreous haze (VH) 0 response at Month 5 based on subjects who were randomized, received at least one dose of IP at baseline, and reached or completed Month 3 visit of the study. Missing VH status at the interim analysis will be handled using the multiple imputation approach in the similar manner as specified in Section 8.2.1. However, only number of enrolled eye will be used as the stratification factor in the Cochran-Mantel-Haenszel (CMH) test procedure (Yu et al., 2020).

The conditional power at the interim analysis, denoted by $CP_{\delta_1}(z_1, \widetilde{n_2})$, can be defined by the following equation (Mehta et al., 2011):

$$CP_{\widehat{\delta_1}}(z_1, \widetilde{n_2}) = 1 - \Phi\left(\frac{z_{\alpha/2}\sqrt{n_2} - z_1\sqrt{n_1}}{\sqrt{\widetilde{n_2}}} - \frac{z_1\sqrt{\widetilde{n_2}}}{\sqrt{n_1}}\right)$$

where n_1 is the number of evaluable subjects at the interim analysis, n_2 is the total number of subjects at the final analysis, $\tilde{n_2} = n_2 - n_1$, $z_{\alpha/2} = \Phi^{-1}(1 - \alpha/2)$, and z_1 is the squared root of the CMH test statistic as computed at the interim analysis of n_1 evaluable subjects. Define the estimated treatment difference, $\hat{\delta_1} = \hat{\pi}_{440} - \hat{\pi}_{\text{sham}}$ at interim analysis, where $\hat{\pi}_{440}$ and $\hat{\pi}_{\text{sham}}$ are Mantel-Haenszel weighted response rates of DE-109 440 µg and Sham arms at interim analysis, respectively.

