8.2.1. Primary Analyses

The primary efficacy endpoint, VH 0 response, is defined as having a VH score of 0 at Month 5 (modified SUN scale). For the primary endpoint, the VH 0 response rate will be evaluated in accordance with the following null (versus alternative) hypothesis:

$$H_0: \pi_{sham} = \pi_{440}$$
versus

$$H_A: \pi_{sham} \neq \pi_{440}$$

where π_{sham} and π_{440} denote the response rate for sham and 440 µg DE-109, respectively.

The Cochran-Mantel-Haenszel (CMH) test with Row Mean Scores statistic (Yu et al., 2020), stratified by pooled strata based on the number of enrolled eyes from a subject (one eye or two eyes), baseline systemic (oral) corticosteroid use (yes or no), and region (US or non-US). Such pooling is needed to avoid the situation where subjects in too small strata might all have the same responses (either success or failure); hence, do not contribute to the test. To guarantee that

a pooled stratum has at least one success and one failure, the pooling algorithm will be performed as follows:

- Determine the number of subjects in each stratum, defined by crossing the number of enrolled eyes, baseline systemic corticosteroid use, and region.
- Within each combination of number of enrolled eyes and region, if one or both strata, stratified by corticosteroid use, have less than 25 subjects, then those strata will be pooled.
- Within each stratification factor level based on number of enrolled eyes, if at least one of (pooled/unpooled) strata have less than 25 subjects, then those strata will be pooled together.

The pooling algorithm will be performed based on the available data prior to the unmasking of the randomization. At the interim analysis, only number of enrolled eyes will be used as the stratification factor.

Study eyes will be treated as non-responders if they meet at least one of the following criteria:

- 1. A study eye is rescued due to the protocol-specified worsening of uveitis (Section 8.1.6)
- 2. A subject discontinued from the study due to lack of efficacy or adverse events
- 3. A study eye meets the protocol-specified worsening of uveitis rescue criteria (Section 8.1.6) regardless whether the eye received any rescue therapies

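### As most naturally read, the interim set (subjects who reached or completed Month 3) omits earlier dropouts for lack of efficacy or adverse events, whom the primary analysis counts as non-responders

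*SAP*

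**What the plan says.** SAP 5.5 sets the timing: "An interim analysis is planned when the first 100 subjects complete their Month 5 Visit". SAP 5.5.1 then names the subjects analysed: those randomized, who "received at least one dose of IP at baseline, and reached or completed Month 3 visit of the study". Missing vitreous haze (VH) status at the interim is imputed much as in SAP 8.2.1, and n1 in the conditional-power formula is the number of evaluable subjects. Conditional power below 30% leads to a futility recommendation, 50% to 80% allows up to 100 more subjects, and any other value leaves the sample size unchanged.

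The final analysis has no follow-up condition. The primary estimand (SAP 2.2.1) is defined "in all study eyes that received at least one dose of the study treatment", and the Full Analysis Set (SAP 6.2) is likewise every randomized, dosed eye. SAP 8.2.1 lists among its non-responder criteria: "A subject discontinued from the study due to lack of efficacy or adverse events". Protocol 9.6 states no Month 3 condition and leaves interim detail to the SAP and the DMC charter; the charter is not among the documents.

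**The concern.** Conditional power predicts the final test, so the interim statistic should estimate the same quantity. Here membership of the interim set depends on follow-up after randomization, and leaving early for lack of efficacy or an adverse event is itself a failure under the primary estimand. Someone dosed on Day 1 who leaves the study at Month 1 or 2 for one of these reasons drops out of both numerator and denominator at the interim, then returns as a non-responder at the end. The cross-reference to SAP 8.2.1 does not restore such subjects, because it governs missing VH status among subjects already in the set.

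The loss could differ by arm, so the interim difference could be too large or too small. At stake are the futility recommendation and a possible increase of up to 100 subjects.

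**Working it through.** **Inputs from the documents.** Response rates of 30% and 12%, 80 subjects per arm, 80% power (SAP 3.3); two-sided alpha 0.05 (SAP 5.4); allocation "randomized in a 2:2:1 ratio to three arms", so about 80 of 100 subjects are in the two tested arms, 40 each; n2 = 160.

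**Assumptions.** Dropout before Month 3 (no rate is given), one eye per subject, one stratum.

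**The plan's own figure.** The pooled-variance chi-square formula without continuity correction gives 80 per arm, with power 80.4% at that size. The stated sample size is reproduced.

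**Effect on the expected difference.** Let d1 and d0 be the shares of dosed DE-109 and sham subjects leaving before Month 3 for lack of efficacy or an adverse event. The interim then expects 0.30/(1 − d1) − 0.12/(1 − d0) instead of 0.18:
- 5% in both arms: 0.189 (+5%)
- 10% in both arms: 0.200 (+11%)
- 10% DE-109, 0% sham: 0.213 (+18.5%)
- 0% DE-109, 10% sham: 0.167 (−7%)

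**Effect on conditional power (CP).** SAP 5.5.1 gives

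CP = 1 − Φ{ (1.96√n2 − z1√n1)/√(n2 − n1) − z1√(n2 − n1)/√n1 }.

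At n1 = 80, CP of 30%, 50% and 80% corresponds to z1 of 1.12, 1.39 and 1.81, so the zones are narrow.

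Worked case, 9/40 against 5/40 responders:
- *All dosed subjects kept.* Expected DE-109 responders 40×14/80 = 7; variance 40×40×14×66/(80²×79) = 2.924; z1 = 2/1.710 = 1.170. CP = 1 − Φ(1.602 − 1.170) = 33%: continue unchanged.
- *Four sham non-responders left before Month 3 and are removed (9/40 against 5/36, n1 = 76).* Expected 7.368; variance 2.885; z1 = 1.632/1.699 = 0.961. CP = 1 − Φ(1.791 − 1.010) = 22%: futility.

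Other cases by the same steps:

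| Responders of 40 (DE-109, sham) | CP, all dosed | Early leavers | CP, Month 3 set | Decision |
|---|---|---|---|---|
| 9, 5 | 33% | 4 DE-109 | 54% | continue becomes increase |
| 10, 5 | 53% | 4 sham | 39% | increase becomes no change |
| 10, 5 | 53% | 4 DE-109 | 73% | increase either way |
| 12, 5 | 85% | 4 sham | 74% | no change becomes increase |
| 9, 5 | 33% | 2 in each arm | 36% | same |
| 10, 5 | 53% | 4 in each arm | 60% | same |
| 10, 4 | 77% | 4 in each arm | 82% | increase becomes no change |

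**How often.** These results come from 200,000 simulated interims per scenario, with pooled-variance z, 40 per arm, and leavers drawn from non-responders. Response rates are 30% and 12% unless stated.
- 3% loss in both arms: 2.3% change futility status, 8% change zone.
- 5% in both arms: 3% change futility status, 10.5% change zone.
- 2% DE-109, 5% sham: the overall futility rate stays at about 19%.
- 10% DE-109, 0% sham: the futility rate falls from about 19% to 11% (from 51% to 41% if the true rates are 21% and 12%).
- 0% DE-109, 10% sham: it rises from about 19% to 24%.

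**Check on the counts.** The trigger counts Month 5 completers, so leavers would come on top of the 80 rather than out of them. Take 9/40 against 5/40 as the observed Month 3 set (CP 33%) and add four DE-109 failures: 9/44 against 5/40, n1 = 84. Expected 44×14/84 = 7.333; variance 40×44×14×70/(84²×83) = 2.945; z1 = 1.667/1.716 = 0.971. CP = 1 − Φ(1.823 − 0.924) = 18%. The size of the shift is similar.

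**The case against.** **The wording can be read another way.** If *reached* meant attended, it would add little to *completed*. It may mean that the Month 3 time point has arrived, in which case early leavers stay in and nothing is lost. This stands as a real ambiguity. A reader might infer that the exclusion is certain, but the text does not settle it. It leans towards exclusion: SAP 5.5.1, describing the final double-masked analysis, expressly includes subjects who discontinued early, and the interim rule has no such words.

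**Few subjects are affected.** Only leaving the study before Month 3 counts. Subjects off treatment are encouraged to keep attending (Protocol 7.1), and rescue is available within the study. Subjects in either group who remain under follow-up stay in the set. Protocol 7.2 expects withdrawal to be uncommon. All of this stands and limits the likely size.

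**The large effects need extreme inputs.** Losing about 4 of 40 from one arm and none from the other, within three months and for two reasons only, is an illustration. A reader might infer a known bias in favour of DE-109, or a pattern of adverse events on one arm and lack of efficacy on the other. The documents give no rates by arm, so neither follows.

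**Consequences are bounded.** A reader might also infer that the trial's result is compromised. It is not: the final set, estimand and test do not change, the study *may* stop under the SAP and the DMC *could* recommend stopping under Protocol 9.6, and the DMC may review unmasked efficacy and safety data.

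**Imputation needs data.** Month 3 attendance might be wanted so that imputation has VH scores to use. That does not justify leaving these subjects out, because their status is already fixed as non-response.

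**Conclusion.** The point holds in conditional form. As most naturally read, SAP 5.5.1 leaves out known failures, and its conditional power then refers to subjects who stayed to Month 3 rather than to all dosed eyes. If *reached* means that the due date has passed, there is no discrepancy, but the SAP does not say so, and two teams could reach different recommendations from the same data.

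The size depends on assumed dropout. It is small for equal losses of 5% or less per arm, although a result close to a cut-off can still change zone. One-sided losses near 10% shift conditional power by roughly 10 to 20 points, in a direction set by which arm loses more. These figures ignore two-eye subjects and are scenarios, not forecasts. Only the interim recommendation is affected. The change is worth making because that recommendation governs stopping or enlarging the trial and the rule is cheap to settle before unmasking.

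**What to change.** In SAP 5.5.1 and the DMC charter, replace the Month 3 condition with: all randomized and dosed DE-109 440 µg and sham subjects whose scheduled Month 3 date (Day 90, counted from Day 1) falls on or before the interim data cut-off, whether or not they remain in the study.

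Within that set:
- apply the SAP 8.2.1 non-responder rules to subjects who discontinued for lack of efficacy or an adverse event, and to eyes that met the rescue criteria;
- impute those who left for other reasons;
- count all of them in n1.

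Using the due date also keeps out recent early leavers whose contemporaries are not yet due, so failures are not over-counted. Subjects between Month 3 and Month 5 stay in, as the SAP now has it.

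The cost is a short text change and a small amount of programming, with no new data or subjects. Interim response rates will be slightly lower.

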2.3. Benefit/Risk Assessment

Two Phase III studies have been completed (SAKURA Program: SAKURA Study 1 and SAKURA Study 2) which evaluated three doses of DE-109 (44 µg, 440 µg, and 880 µg, each administered every 2 months) in subjects with active NIU-PS. A total of 590 randomized, treated study eyes (590 subject IDs, 589 subjects) received at least one injection of DE-109 (i.e., integrated Safety population). In the integrated Safety population of the two studies, 459 treated study eyes were exposed to the 440 or 880 µg dose of DE-109 for at least 6 months (defined as staying in study under either dose for at least 173 days after the first 440 or 880 µg dose) and 318 treated study eyes were exposed to the 440 or 880 µg dose for at least 1 year (defined as staying in study for at least 346 days after the first 440 or 880 µg dose). The DE-109 440 µg dose exhibited the optimal benefit/risk profile in Study 1 and performed similarly in Study 2. The efficacy and safety data in these large Phase III studies support the 440 µg dose as the most appropriate dose of DE-109 for treating active NIU-PS. For the primary endpoint (VH score of 0 at Month 5), the response rate in the 440 µg dose group was appreciable and consistent across the two studies (22.8% and 19.1% in Study 1 and Study 2, respectively).

The safety data from the SAKURA program demonstrated a reasonable safety profile of the 440 μ g dose of DE-109, with few risks directly related to its use. Risks associated with the use of DE-109 are non-infectious endophthalmitis, which was observed mostly with the 880 μ g dose and successfully treated with corticosteroids and surgical intervention, and the presence of drug depot in the visual axis, which, if it occurs, is a self-limiting event that may resolve as the drug depot dissolves and moves out of the visual axis. At all three doses (44 μ g, 440 μ g, and 880 μ g, each administered every 2 months), DE-109 had minimal effect on IOP with repeat dosing and the systemic exposures after intravitreal dosing were well below the levels required for immunosuppression, thereby minimizing the possibility of systemic side effects.

The undisclosed, fixed dose of DE-109 in the Dummy arm will be within the range of doses evaluated in the previous Phase III studies (44 μ g to 880 μ g), all of which have demonstrated an acceptable safety profile.

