9.6. Interim Analyses, Primary Analysis, and Analysis of Open-Label Period of Study

An interim analysis is planned when the first 100 subjects complete their Month 5 Visit. There are two goals for this interim analysis (1) to assess for futility; and (2) to re-assess the sample size. Sample size re-assessment will be performed with the "promising zone" approach as follows (Mehta et al., 2011). If the conditional power at the interim analysis is between 50% and 80%, the suggested sample size increase may be up to 100 subjects (i.e., 50% of the original sample size). If, on the other hand, the conditional power is > 80% or < 50%, no change to the sample size will take place. If the conditional power is < 30%, then the DMC could recommend stopping the trial due to futility. The DMC could recommend stopping the trial due to safety concerns at any of the DMC meetings and the interim analysis of unmasked data and the DMC will review the results and make recommendations based on the findings. The planned interim analysis will be specified in greater detail in the SAP and in the DMC charter.

The primary analysis of this study is the analysis of the data from the 6-month, double-masked period. These data will be quality-checked, soft-locked, and the primary analysis will be conducted after all subjects have completed the Month 6 visit or prematurely discontinued from the study prior to Month 6. An interim clinical study report will be written documenting the primary analysis results.

Analysis of the open-label period of the study will be performed after the end of the study and documented in the final clinical study report.

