Study eyes which were rescued due to worsening of uveitis specified under previous protocol version but did not meet the rescue criteria under the current version will be treated as rescued due to other reason and censored the data after being rescued. The multiple imputation-based approach will be applied to impute missing VH score data of study eyes which were not rescued and treated as non-responders. The VH 0 response status will then be determined based on the observed or imputed VH score.

For missing VH score due to any other reasons other than protocol-specified worsening of uveitis, the multiple imputation approach will be applied as follows:

- 1. Use Markov chain Monte Carlo (MCMC) to create monotone missingness first with VH score on the logarithm scale. Then obtain standard multiple imputations under MAR assumptions for missing VH scores using monotone regression on the logarithm scale. The imputed values will be then converted into an eligible VH score based on the absolute distance. The missing data are filled in and 50 complete datasets are created. The seed that will be used in the SAS program is 135711.
- 2. Each of 50 complete datasets will then be analyzed separately. The CMH test statistic, response rate for each treatment group, and the rate difference will be calculated for each complete sets.
- 3. The final CMH test statistic, obtained from each complete dataset, will be transformed using Wilson-Hilferty transformation and combined for inference purposes (O'Kelly et al., 2014). Rates and rate differences will also be combined without any transformations.

The Mantel-Haenszel weighted response rate (%) of each treatment group, the Mantel-Haenszel weighted rate difference, the corresponding asymptotic 95% confidence interval (CI) and the CMH's p-value will be reported.

The main part of the SAS code for the specified CMH test procedure and the multiple imputation are provided in Appendix C, respectively.

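### SAP 5.5.1 gives the interim z1 no sign, so a result against DE-109 can escape the futility flag or fall in the zone that adds subjects

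*SAP*

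**What the plan says.** SAP Section 5.5.1 gives a conditional power formula driven by z1, which "is the squared root of the CMH test statistic as computed at the interim analysis". The next sentence defines an estimated treatment difference, 440 µg minus sham, from Mantel-Haenszel weighted rates. That difference labels CP as a subscript but does not appear on the right-hand side of the formula.

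The zones depend on conditional power alone:

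- Below 30%: "If the conditional power is less than 30%, futility will be recommended and the study may stop for futility".
- From 50% to 80%: "If the conditional power is between 50% and 80%, the sample size will be increased up to 100 extra subjects".
- From 30% to 50%, or above 80%: the sample size stays as it is.

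Missing data at the interim follow SAP Section 8.2.1, where the CMH statistic from each imputed dataset "will be transformed using Wilson-Hilferty transformation and combined for inference purposes". Protocol Section 9.6 has the same cut-offs, no formula, and the statement "The planned interim analysis will be specified in greater detail in the SAP and in the DMC charter".

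**The concern.** For two arms the CMH row mean scores statistic is a chi-square on one degree of freedom, tested against a not-equal alternative. Its square root measures the size of the difference and not its direction. The conditional power formula needs direction, because it asks how likely the trial is to finish in favour of DE-109. With an unsigned z1, the larger the effect against DE-109, the higher the calculated conditional power.

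No separate rule covers an adverse interim result, so the zones inherit the problem. An independent team following the text exactly could report no futility signal, or a sample size increase, for a drug doing worse than sham. The DMC would then have to override a pre-specified rule to reach the sensible conclusion.

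**Working it through.** **Inputs.** Two-sided alpha 0.05, so z = 1.960 (SAP Section 5). Interim at 100 of 200 subjects, allocation 2:2:1, so about 80 of 160 in the two compared arms; n1/n2 = 0.5 either way. Design rates 30% and 12% (SAP Section 3.3). Earlier 440 µg response rates: "22.8% and 19.1% in Study 1 and Study 2, respectively" (Protocol Section 2.3).

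**The plan's own figure.** The plan states no z1 cut-offs to reproduce. Its sample size does reproduce: 30% vs 12% at 80 per arm gives 80.4% power by the Pearson chi-square test without continuity correction.

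**Cut-offs.** The SAP formula is

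CP = 1 − Φ{ [1.960·√n2 − z1·√n1]/√(n2−n1) − z1·√(n2−n1)/√n1 }.

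At n1/n2 = 0.5 this becomes CP = 1 − Φ(2.7718 − 2·z1), so z1 = [2.7718 − Φ⁻¹(1−CP)]/2:

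- CP 30%: (2.7718 − 0.5244)/2 = 1.124 (two-sided p = 0.26)
- CP 50%: 2.7718/2 = 1.386 (p = 0.17)
- CP 80%: (2.7718 + 0.8416)/2 = 1.807 (p = 0.07)

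With the sign attached, z1 = −1.124, −1.386 and −1.807 give CP of 2.6×10⁻⁷, 1.5×10⁻⁸ and 8.6×10⁻¹¹.

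The interim set also admits subjects who have got only as far as Month 3, so n1 may exceed half of n2. With n2 = 200 the cut-offs are 1.26/1.52/1.93 at n1 = 120 and 1.47/1.70/2.06 at n1 = 150. They shift, but the problem remains.

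**Example.** 4/40 on DE-109 and 9/40 on sham, single stratum. The pooled rate is 13/80 = 0.1625, and z = −0.125/√(0.1625×0.8375×2/40) = −1.515. The CMH factor √(79/80) makes it −1.506. As written, CP = 1 − Φ(2.7718 − 3.012) = 59.5%, in the zone that adds subjects. Signed, CP = 1 − Φ(2.7718 + 3.012) = 3.7×10⁻⁹.

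**Does Section 8.2.1 restore direction?** The one-degree-of-freedom Wilson-Hilferty value is (∛χ² − 7/9)/√(2/9). For 4/40 vs 9/40, χ² = 2.268 and the value is (1.314 − 0.778)/0.471 = +1.14. Swapping the arms gives the same value. It turns negative only when χ² is below (7/9)³ = 0.47, that is |z| below 0.69. A negative value therefore marks a small difference, not an adverse one.

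**How often it matters.** Exact enumeration of all 41×41 outcomes with 40 per arm, one eye per subject, complete data and one stratum. The last three columns give the probability that the result is against DE-109 and the CP as written lies in the stated zone.

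| True rates, 440 µg vs sham | CP < 30%, as written | CP < 30%, signed | Adverse, 30–50% | Adverse, 50–80% (adds subjects) | Adverse, > 80% |
|---|---|---|---|---|---|
| 30% vs 12% | 18.9% | 19.0% | 0.05% | 0.03% | 0.01% |
| 22.8% vs 12% | 42.8% | 43.6% | 0.4% | 0.3% | 0.1% |
| 19.1% vs 12% | 57.1% | 59.5% | 1.2% | 0.8% | 0.4% |
| 12% vs 12% | 73.2% | 86.6% | 5.4% | 4.8% | 3.3% |
| 12% vs 20% (assumed) | 53.7% | 98.2% | 10.4% | 14.2% | 19.8% |

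The last row is an assumption not taken from the documents; it shows what happens if DE-109 is truly worse than sham.

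**The case against.** The best counter-argument is that a signed z1 was plainly meant. The formula is one-tailed, CP is indexed by the estimated difference, that difference is defined as 440 µg minus sham, and the trial tests superiority. Section 8.2.1 also produces each arm's rate and the signed rate difference, and the DMC sees unmasked data. Futility is advisory: the SAP says the study may stop, and the Protocol says "If the conditional power is < 30%, then the DMC could recommend stopping the trial due to futility". At response rates drawn from the documents, the chance of a futility flag changes by at most about 2.4 points (57.1% against 59.5%).

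Most of this stands. The intent is probably as described, the direction is available to anyone who looks, and the harmful-drug scenario should carry little weight. But no supplied passage attaches the sign to z1, and the SAP wording for the 50–80% zone is that the sample size will be increased. Futility rules exist chiefly for a drug that does not work, and in that case the gap is 86.6 − 73.2 = 13.4 points. The charter and code may well be right, but neither can be seen: Section 8.2.1 says "The main part of the SAS code for the specified CMH test procedure and the multiple imputation are provided in Appendix C", and that appendix is not in the supplied text.

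**Conclusion.** The concern holds. As worded, SAP Section 5.5.1 treats equal effects for and against DE-109 alike. At n1/n2 = 0.5, adverse results with |z1| above 1.124 miss the futility flag, and those from 1.386 to 1.807 point to adding subjects, although their properly signed conditional power is below 0.0001%.

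The consequence is limited: negligible at the design rates, up to about 2.4 points at the earlier trials' rates, and 13.4 points with no true effect. These probabilities assume 40 per arm, one eye per subject, complete data and a single stratum; the planned interim test stratifies by number of eyes and uses imputation. The finding concerns the SAP text, not what would actually be run, and the wording should be corrected.

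**What to change.** In SAP Section 5.5.1, define z1 as the sign of the estimated difference (440 µg minus sham, Mantel-Haenszel weighted, pooled over imputations) multiplied by the square root of the CMH statistic. Where CMH statistics are combined by Wilson-Hilferty, take the combined p-value, find the one-degree-of-freedom chi-square with that p-value, take its square root, and then attach the sign.

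Every result against DE-109 then falls in the below-30% zone. At z1 = 0, CP = 1 − Φ(1.960·√[n2/(n2−n1)]), which is 0.3% at n1/n2 = 0.5 and below 2.5% at any fraction. No threshold changes.

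Confirm that the DMC charter and the Appendix C code use the same definition. The cost is one or two sentences and that check, with no operational effect.
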